4.7.6 Daily measurement of patch adhesion as recorded in the subject diary

Frequency counts (and percentages) for the patch adhesion score collected at each clinic visit will be summarized by visit, along with the best adhesion score (i.e., lowest patch adhesion score per subject) and the worst adhesion score (i.e., highest patch adhesion score per subject).

The mean of the patch adhesion scores collected from Day 1 to Day 29 will be calculated for each subject. The mean patch adhesion score will be summarized using descriptive statistics for the entire treatment period. The mean of each subject's best adhesion score and worst adhesion score will also be summarized.

4.7.7 Abaloparatide-sMTS Released Dose

A released dose is defined as “Initial Patch Content – Residual drug amount from Swab and Patch.” Descriptive statistics will be provided to summarize the released dose, the percentage of released dose to nominal dose, the percentage of release dose to initial patch content, the residual drug amount from the patch, the residual drug amount from the patch and swab, by visit. Released dose values that are negative will be set to 0 in the summaries, but the recorded values will be presented in the listings.

4.7.8 Daily measurement of user errors as recorded in the subject diary

The following summary statistics will be provided.

4.7.8.1 Summary of patch application by study day

- Frequency counts (and percentages) for the successful first application
- Frequency counts (and percentages) of the application location for the successful application
- Descriptive statistics for the time from removal from refrigerator until application – data from successful application is used
- Descriptive statistics for the time from patch application until removal – data from successful application is used

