#### **Secondary:**

- The secondary objective is to evaluate the usability of abaloparatide-sMTS as measured by incidence of user errors, overall subject acceptability, preference, satisfaction and adherence to study therapy.
- Other secondary objectives include an evaluation of overall safety and tolerability of abaloparatide-sMTS as assessed by treatment emergent adverse events (TEAEs), vital signs (orthostatic blood pressure, pulse rate, body temperature, and respiration rate), ECGs, laboratory tests (chemistry, hematology, urinalyses) and local tolerance.

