## 5.1.1. Abaloparatide-sMTS

The abaloparatide-sMTS is enclosed in a collar assembly for loading onto a spring-loaded applicator. The abaloparatide-sMTS dose will be 300 µg.

Abaloparatide-sMTS is stored refrigerated at 2° to 8°C (36° to 46°F). The abaloparatide-sMTS will be removed from refrigeration approximately 1 hour prior to application. Please refer to the pharmacy manual for further details.

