## 5.5. Dosing and Administration

The first self-administration of abaloparatide-sMTS will occur at the study site on Day 1, under observation.

Subjects will be trained by study personnel to self-administer study medication with the abaloparatide-sMTS patch and applicator; a single daily dose of 300 µg of abaloparatide-sMTS will be applied to the thigh for 5 minutes during the treatment period following the Instructions for Use. Please refer to the pharmacy manual for additional details on study drug administration.

The subject is to remain under observation for a minimum of 60 minutes after abaloparatide-sMTS. On the days when blood sampling is required after study medication administration, the subject is to remain at the vicinity of the clinic for the blood collections scheduled up to 4 hours after abaloparatide-sMTS application. Subjects are to be instructed to self-administer abaloparatide-sMTS application at a location where they have the ability to sit or lie down.

At each clinic visit during the Treatment Period, any used and unused abaloparatide-sMTS should be returned.

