1.2.5.2 Secondary Endpoints

Pharmacodynamic Endpoints

Pharmacodynamic endpoints include:

- Change, percent change from baseline, and ratio from baseline to Day 15 and Day 29 in s-PINP.
- Change and percent change in serum calcium (albumin-corrected) from baseline to each post-dose timepoint.
- Change and percent change in serum phosphorus from baseline to each post-dose timepoint.
- Change and percent change in cAMP from baseline to each post-dose timepoint.

Other Endpoints

Other endpoints include subject/investigator-reported outcomes:

- Investigator assessment of signs of local skin reaction using a 4-point scale at Day 1, Day 15 and Day 29
- Subject assessment of symptoms of local skin reaction using a 4-point scale from Day 1 through Day 29 as recorded in the subject diary
- Subject satisfaction and convenience of treatment as measured by Treatment Satisfaction Questionnaire for Medication (TSQM9) at Day 15 and Day 29
- Subject acceptability measurement (5-point Likert Scale) at Day 1, Day 15 and Day 29
- Subject preference for treatment attributes at Day 1, Day 15 and Day 29
- Daily measurement of patch adhesion as recorded in the subject diary
- Daily measurement of user errors as recorded in the subject diary

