4.7.8.2 Summary of patch application during the treatment period

- Descriptive statistics for the first application success rate; success rate (%) is defined as number of successful first application / total number of applications for the subject x 100.
- Descriptive statistics for mean time from removal from refrigerator until application; time averaged over the treatment period for the subject; data from successful application is used for the subject mean
- Descriptive statistics for the mean time from patch application until removal; time averaged over the treatment period for the subject; data from successful application is used for the subject mean

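### The user-error summaries give no treatment-period incidence for misplaced or mistimed applications, and none for any user error overall; location and times are limited to applications called successful, a term the SAP does not define

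*SAP*

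**What the plan says.** The protocol synopsis gives one secondary objective as to "evaluate the usability of abaloparatide-sMTS as measured by incidence of user errors", alongside acceptability, preference, satisfaction and adherence. SAP 1.2.5.2 lists the matching endpoint: "Daily measurement of user errors as recorded in the subject diary".

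The protocol states three conditions of use that a diary entry can be checked against. Under Protocol 5.5 the dose "will be applied to the thigh for 5 minutes during the treatment period following the Instructions for Use". Under Protocol 5.1.1 the patch "will be removed from refrigeration approximately 1 hour prior to application".

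SAP 4.7.8.1 (by study day) plans "Frequency counts (and percentages) of the application location for the successful application". For refrigerator-to-application time and for wear time it plans descriptive statistics in which "data from successful application is used". SAP 4.7.8.2 (treatment period) summarises each of the two times as a subject-level mean: "time averaged over the treatment period for the subject; data from successful application is used for the subject mean".

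The same section also reports first-application success by day and as a rate per subject. SAP 4.7.8.3 to 4.7.8.6 tabulate application difficulties and cleaning steps from all available data, with no success restriction.

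**The concern.** Site, wear time and warm-up time are the conditions of use for which the protocol gives an explicit reference. A patch placed elsewhere, removed early or late, or applied too soon after refrigeration is a natural candidate for a user error. For these three items the SAP describes a selected set of applications and does not say how many departed from the instructions.

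The consequence falls mainly on home use. Only Days 1, 15 and 29 are dosed at the site, where Protocol 5.6 has administration supervised, and PK is sampled only on those days. The other 26 of 29 planned applications are at home, where the diary is the direct record of how the patch was used. If its location and timing data are filtered by an undefined flag and then averaged, the report cannot say how often, or in how many women, self-administration departed from the instructions on these items.

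**Working it through.** The documents give no user-error rate, no tolerance and no power calculation, so there is no planned figure to reproduce. The check sets the planned summaries against the protocol's conditions of use, then uses illustrative data with 29 applications per subject and a 5-minute reference.

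**Step 1. What is planned for each item**

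| Item | Protocol reference | SAP 4.7.8.1, by day | SAP 4.7.8.2, treatment period | Count of departures |
|---|---|---|---|---|
| Location | Thigh | Frequencies, successful only | None | No total by application or subject |
| Wear time | 5 minutes | Descriptive statistics, successful only | Subject mean, successful only | None |
| Warm-up time | About 1 hour | Descriptive statistics, successful only | Subject mean, successful only | None |
| Any user error | – | None | None | None |

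SAP 4.7.8.3 to 4.7.8.8 cover difficulties, cleaning and the 24-hour skin mark. None of them fills the last column.

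**Step 2. If *successful* includes correct use**

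Mistimed applications leave the time summaries. Suppose 3 of 29 patches are removed at 1 minute and classed as unsuccessful, and 26 are worn 5 minutes.

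- Planned subject mean: 26 × 5 / 26 = 5.00 minutes.
- Mean over all 29: (26 × 5 + 3 × 1) / 29 = 133 / 29 = 4.59 minutes.
- Mistimed: 3 / 29 = 10.3%.

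If these were first attempts, the first-application success rate would fall to 26 / 29 = 89.7% without replacement patches, or 26 / (29 + 3) = 81.3% if each was replaced. The failure is visible, but its link to wear time is not.

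**Step 3. If *successful* means only that the dose was applied**

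Mistimed applications stay in, uncounted, and can cancel in the subject mean.

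- 14 at 3 minutes and 15 at 7 minutes: (14 × 3 + 15 × 7) / 29 = 147 / 29 = 5.07 minutes, with all 29 off the 5-minute reference.
- 10 at 1 minute, 10 at 9 and 9 at 5: (10 + 90 + 45) / 29 = 5.00 minutes, with 20 / 29 = 69.0% off it.

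Errors in one direction do not cancel: if the 3 one-minute applications of Step 2 are kept in, the mean moves to 4.59.

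**Step 4. What the by-day table would show**

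Take 22 subjects on one day: three at 1 minute, three at 9 and sixteen at 5.

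- Mean: (3 + 27 + 80) / 22 = 5.00 minutes.
- SD: √[(3 × 16 + 3 × 16) / 21] = 2.14.
- Quartiles 5 and 5; minimum 1, maximum 9.

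The spread shows that something departed from 5 minutes. It does not show that 6 of 22 applications did, or whether the same women are affected from day to day.

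**The case against.** The strongest reply is that user errors are already well covered. Dropped patches, touched patches, pouch difficulty, hand washing, site cleaning and leg dryness are tabulated by day and per subject with no success filter. First-application success appears in the same sections as the filtered times. Detachment is scored separately (Protocol 6.6.4), with worst scores summarised under SAP 4.7.6. SAP 3.10 lists all available data, and the synopsis promises only a descriptive tabulation of user errors. This stands. A reader might infer that the secondary objective is not produced at all, or that user errors in general are removed; the documents do not support either.

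The reply can also question the meaning of *successful*. SAP 4.3 takes the number of doses received from the count of successful applications, and Protocol 5.3 has a damaged patch replaced with a new one. The word may therefore identify the patch that delivered that day's dose, whatever the technique. A reader might infer that the tables will look on target by construction. That holds only if mistimed wear is classed as unsuccessful, which no passage says.

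Third, the averaging is limited. Location is a frequency count, so an off-thigh site in a successful application would show on its day if the diary form offers that category. The by-day times are not averaged within subject, and Protocol 8.4.1 calls for SD, quartiles, minimum and maximum. Cancellation affects only the two treatment-period time summaries.

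None of this supplies the missing counts. It narrows the point to three items and one overall figure.

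**Conclusion.** The narrower point holds under either meaning of *successful*. Mistimed applications are either dropped from the time summaries or kept, uncounted, and able to cancel in the subject mean. The SAP plans no incidence of mistimed wear or mistimed warm-up, no total for off-thigh placement, and no overall any-user-error incidence, although the synopsis names incidence of user errors as a measure of usability.

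The real size cannot be computed, because the documents give neither error rates nor tolerances. The examples assume 29 applications per subject and invented wear times; they show what the planned summaries could hide, not what they will. The point does not affect the PK primary endpoint. In a descriptive, hypothesis-generating study of about 22 subjects it is a change the sponsor should make, not a flaw that invalidates the study.

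**What to change.** 1. Define *successful* application in SAP 4.7.8, and confirm that the same meaning applies to doses received in SAP 4.3.
2. Over every application with the item recorded, successful or not, report the number and percent of applications, and of subjects with at least one:
   - (a) off the thigh;
   - (b) with wear time outside prespecified limits;
   - (c) with refrigerator-to-application time outside prespecified limits;
   - (d) with any recorded user error.
3. Have the sponsor set the limits for (b) and (c) from the Instructions for Use before the data are summarised.
4. Show home and clinic applications separately. The study-day tables do this only in part: visits have a ±2-day window, and the treatment-period summaries pool both settings.
5. Keep the planned success-only summaries as a secondary display.

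The cost is SAP wording and one extra table from diary items the SAP already plans to summarise. The diary form is not in the documents, so the sponsor should confirm that site and times are recorded for unsuccessful attempts. Wear time may not exist for a patch that never adhered; count these as failed applications rather than letting them drop out as missing. The usability figures may look less favourable.

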4.7.8.2 Summary of patch application during the treatment period

- Descriptive statistics for the first application success rate; success rate (%) is defined as number of successful first application / total number of applications for the subject x 100.
- Descriptive statistics for mean time from removal from refrigerator until application; time averaged over the treatment period for the subject; data from successful application is used for the subject mean
- Descriptive statistics for the mean time from patch application until removal; time averaged over the treatment period for the subject; data from successful application is used for the subject mean

4.7.8.3 Summary of patch application difficulties by study day

Frequency counts (and percentages) for items related to patch application difficulty will be provided using the available data collected at the study day

- Steps with difficulty
- Difficulty opening pouch
- Patch falls on floor
- Touch patch before application
- Difficulty caused by pain
- Difficulty caused by other issues

4.7.8.4 Summary of patch application difficulties during the treatment period

Descriptive statistics for the following items per subject will be provided using the available data collected at the study day

- Number of steps with difficulty
- Percentage of with difficulty opening pouch
- Percentage of patch falling on floor
- Percentage of patch touched before application
- Percentage of difficulty caused by pain
- Percentage of difficulty caused by other issues

4.7.8.5 Summary of patch application cleaning by study day

Frequency counts (and percentages) for items related to patch application cleaning will be provided using the available data collected at the study day

- Wash hands before applying
- Clean and inspect application site
- Clean applicator afterwards
- Leg dry before application

4.7.8.6 Summary of patch application cleaning during the treatment period

Descriptive statistics for items related to patch application difficulty will be provided using the available data collected at the study day

- Percentage of washing hands before applying
- Percentage of cleaning and inspecting application site
- Percentage of clean applicator afterwards
- Percentage of leg dry before application

4.7.8.7 Summary of 24-hour skin assessment by study day

Frequency counts (and percentages) of subjects who still identify a clear mark after 24 hours where the patch was applied will be provided.

4.7.8.8 Summary of 24-hour skin assessment during the treatment period

Descriptive statistics for items related to 24-Hour skin assessment will be provided.

- Percentage of applications where a clear mark is identified per subject
= number of “Yes” for the question (Can you still identify a clear mark where the patch was applied?) / total number of applications for the subject x 100

Frequency (and percentage) of responses where a clear mark is identified across all subjects in the study

Percentage

= Total number of “Yes” for the question across all subjects in the study /
Total number of applications across all subjects in the study x 100

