- 11. All subjects will have a urine drug screen for drugs of abuse and alcohol performed on the Screening Period (Visit 1), and on Day 1 (Visit 3).
- 12. When necessary, re-training may be done post Day 1 / Visit 3.
- 13. Study drug is self-administered daily beginning Day 1 (Visit 3) through Day 29 (Visit 5/EOT), inclusive. On Days 1, 15, and 29, subject will self-administer abaloparatide-sMTS at the study site.

- 14. BMD measured by DXA at Screening visit if most recent DXA was done over 12 months prior to screening.
- 15. Investigators will perform an assessment of the application site at each clinic visit prior to application of abaloparatide-sMTS, 5 minutes after application (ie, immediately upon removal of the patch), and 1- hour following abaloparatide-sMTS application. Signs of local skin reactions will be assessed using a 4-point scale, as described in Section 6.6.2.1.
- 16. The subject will maintain a diary to record their assessment of symptoms of local skin reactions for 29 days beginning on Day 1 (Visit 3). The subject will evaluate the application site prior to study drug administration, 5 minutes after application (ie, immediately upon removal of abaloparatide-sMTS), and 1 hour after abaloparatide-sMTS application. Symptoms of local skin reactions will be assessed using a 4-point scale as described in Section 6.6.2.2.
- 17. Subject assessment of patch adhesion immediately prior to abaloparatide-sMTS removal on each day of the treatment period from Day 1 (Visit 3) to Day 29 (Visit 5/EOT).
- 18. An assessment of pain (separate from the pain question on the 4-point scale for local tolerance) will be done after sMTS application.
- 19. The Subject Diary will be reviewed by study personnel at each study visit to ensure subject compliance.
- 20. AEs and SAEs will be recorded on the case report forms starting from the signing of the informed consent until 7 days after the last dose of study medication. All treatment-related AEs will be followed until resolution or stabilization. Any SAEs that occur at any time after completion of the study, which are considered by the investigator to be related to study treatment, must be reported to the Sponsor or its designee.

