4.8.2 Laboratory Data

Clinical laboratory values will be provided in standard international (SI) units by the central laboratory.

Summaries of laboratory data using descriptive statistics by study visit will be presented based on the SI units, including absolute results and changes from baseline. This includes serum chemistry, hematology, coagulation, urinalysis, and additional tests. In the event of repeat or unscheduled assessments, the last non-missing value per study day/time will be used in the summary statistics.

Shift analyses of laboratory data from baseline to post-baseline (day 15 and day 29, respectively) will be performed. Results for laboratory data will be presented by category (above normal limit, within normal limit, below normal limit). For shift tables, subjects who are missing either assessment will not be included in the percentage calculation (numerator or denominator).

All laboratory data, including repeated values and results from unscheduled visits, will be presented in data listings, with indication of higher or lower than the associated normal range of each laboratory test.

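### SAP 4.7.8.8 divides Yes answers by all applications, so a blank 24-hour mark answer counts as No and the reported rate is only a lower bound

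*SAP*

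**What the plan says.** SAP 4.7.8.8 gives two treatment-period figures for the 24-hour skin question.

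- **Per subject.** The number of Yes answers is divided by the subject's applications; the formula ends "Can you still identify a clear mark where the patch was applied?) / total number of applications for the subject x 100". Its label also speaks of applications.
- **Pooled.** The line is introduced as "Frequency (and percentage) of responses where a clear mark is identified across all subjects in the study", but its denominator is "Total number of applications across all subjects in the study x 100".

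The by-day table in SAP 4.7.8.7 says only "Frequency counts (and percentages) of subjects who still identify a clear mark after 24 hours where the patch was applied will be provided", with no denominator.

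Other diary summaries in the same part of the SAP are worded differently. In 4.7.8.4 the per-subject statistics "will be provided using the available data collected at the study day". Section 4.7.8.6 opens "Descriptive statistics for items related to patch application difficulty will be provided using the available data".

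The general missing-data rule, SAP 3.10, excludes imputation of pharmacodynamic and safety data unless stated otherwise. It does not address a blank diary item.

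**The concern.** A blank answer adds nothing to the numerator but stays in the denominator, which is how a No behaves. The rate therefore mixes two things: whether the skin still shows a mark, and whether the subject filled in the diary. Two subjects with identical skin can receive different rates because one skipped some answers.

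A reader of the pooled line would take it as a share of the answers given, because its label says so. What is at stake is one descriptive skin item and how it is read. The item sits within the user-error section of the SAP but is not itself named among the endpoints.

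**Working it through.** The documents give no value for this rate and no non-response figure, so there is nothing to reproduce. The check evaluates the printed formula.

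**Inputs**

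- Y = Yes answers, A = answered questions, T = applications.
- T = 29 for a full course: daily dosing from Day 1 to Day 29 inclusive (Protocol Table 1, note 13).
- Share unanswered, u = 1 − A/T: not in the documents; 5%, 10% and 20% are assumed.

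**1. What the formula returns**

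Y/T = (Y/A) × (A/T), that is, the answered-item rate times the share answered. This is an identity. Reading Y/A as the real mark rate needs a further assumption: that skipping the question is unrelated to having a mark.

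| Answered-item rate | u = 5% | u = 10% | u = 20% |
|---|---|---|---|
| 50% | 47.5% | 45.0% | 40.0% |
| 80% | 76.0% | 72.0% | 64.0% |

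For example, 0.80 × 0.90 = 0.720.

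**2. What can be said without that assumption**

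If every blank is No, the rate is Y/T, which is the SAP formula. If every blank is Yes, it is (Y + T − A)/T.

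- 15 Yes, 14 blanks, T = 29: from 15/29 = 51.7% to 29/29 = 100%.
- 14 Yes, 20 answered, T = 29: from 14/29 = 48.3% to (14 + 9)/29 = 79.3%, with an answered-item rate of 14/20 = 70.0%.

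The SAP figure is always the lower end.

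**3. The Day 29 application**

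Protocol Table 1, note 16, says "The subject will maintain a diary to record their assessment of symptoms of local skin reactions for 29 days beginning on Day 1", and note 24 has the diary returned at that visit. If the 24-hour question is not asked for the Day 29 patch, a subject with a mark after every application scores at most 28/29 = 96.6%. With Visit 5 at the edges of its ±2-day window, the maximum is 26/27 = 96.3% or 30/31 = 96.8%. Pooled over 22 completers it is (22 × 28)/(22 × 29) = 616/638 = 96.6%.

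**The case against.** **The per-subject line matches its own label.** It promises a percentage of applications and divides by applications. This stands: the mismatch between label and formula is in the pooled line only. A blank is still scored as No in both.

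**The comparators are imperfect.** The sentence in 4.7.8.6 heads a cleaning table but speaks of difficulty, so it may be carried-over wording. The laboratory rule in SAP 4.8.2, that "subjects who are missing either assessment will not be included in the percentage calculation (numerator or denominator", concerns shift tables that need two values per subject and is not a general rule. Both points are fair. The comparators show that available data is the neighbouring convention, not that 4.7.8.8 breaks a binding rule.

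**Non-response may be small.** Staff review the diary at each visit and missing data are queried. If applications are counted from the same diary, as doses are in SAP 4.3, a wholly blank day drops out of both parts of the fraction. Dilution then needs a recorded application with a blank mark answer. This limits the size but does not alter the formula.

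**Answered-only rates can also be biased.** If subjects skip the question because there is, or is not, a mark to report, the answered-item rate errs in an unknown direction. This stands, and it is why bounds are needed beside it.

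**A reader might infer that the Day 29 patch cannot be answered.** The documents do not establish that. The diary form is not among them and the question is not in the Schedule of Assessments. Protocol 6.2.7.3 and 6.6.2.1 also provide for checks every 24 hours after Day 29 for subjects with reactions. Those checks are not the mark question, but they show that later contact exists. Day 29 is therefore a point to settle, not a shown fault.

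**Conclusion.** The point holds as a minor one. As written, SAP 4.7.8.8 scores an unanswered question as No, per subject and pooled, and the pooled label does not describe its own denominator. The direction is certain: the reported figure cannot exceed the answered-item rate and is the lower bound on the mark rate. The size is not known. An assumed 10% unanswered turns 80% into 72.0%, and that gap measures bias only if skipping is unrelated to the mark.

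Three stronger readings are not supported:

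- **That 15 Yes and 14 blanks should read 100%.** The data allow anything from 51.7% to 100%.
- **That the compliance rate in SAP 4.3 has a similar error because it stops at the last dose.** It is a legitimate on-treatment measure with its formula printed. Early stopping shows in disposition (SAP 4.1) and in exposure duration. Counting withdrawn subjects to Day 29 would mix discontinuation with dosing behaviour.
- **That the first-application success rate in SAP 4.7.8.2 is wrong because it too divides by applications.** Nothing beyond a possible clarification of its denominator follows.

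No listed endpoint and no primary PK result is affected.

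**What to change.** - **SAP 4.7.8.8:** use applications with a non-missing 24-hour answer as the denominator, per subject and pooled, and reword the per-subject label to match. The pooled label then fits as it stands.
- **Beside each rate:** report the number unanswered and the two bounds, all blanks No (the present formula) and all blanks Yes. Show a subject with no answers as not calculable.
- **SAP 4.7.8.7:** state the same denominator for each study day.
- **Day 29:** state whether the question is asked for that application, and leave it out of the denominator if it is not.
- **Optional:** label the SAP 4.3 rate as on-treatment compliance.

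The cost is a few lines of SAP text and small programming changes, with no new data. The drawbacks are that the headline mark rate will be higher than under the present formula wherever answers are missing and at least one answer is Yes, and that it can be biased either way if skipping relates to the mark. The bounds make that uncertainty visible.
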